### Supplemental analyses

#### **DSQ total score:**

Two supplemental analyses for different strategy of use of rescue treatment will be performed:

1. Composite strategy for rescue: Worst observation carried forward (WOCF) approach will be used for data after the use of rescue treatment.
2. Treatment policy for rescue: Data collected after the use of rescue treatment will be included in the analysis.

The missing data will be imputed by the MI method as described in primary analysis for the supplemental analyses above.

#### **5.6.2. Analysis of Secondary Efficacy Variables**

##### Binary endpoints at week 24:

Secondary efficacy endpoints that measure binary responses at week 24 will be analyzed in the same fashion as the co-primary endpoint of histologic response of peak esophageal intraepithelial eosinophil count of  $\leq 6$  eos/hpf, including the method to handle missing data .

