7.3. Rescue Treatments

If medically necessary (eg, for treatment of intolerable EoE symptoms), rescue medications (systemic and/or swallowed topical corticosteroids) or emergency esophageal dilation are allowed for study patients in Parts A, B, and C. An endoscopy with biopsy will be performed prior to the initiation of rescue therapy. Patients who undergo an endoscopy with biopsy due to the initiation of rescue therapy will not undergo the scheduled end of treatment visit endoscopy/biopsy at weeks 24 and 52. Patients who receive rescue treatment during the double-blind period of the study will not be eligible for the extended active treatment period unless an endoscopy with biopsy is performed prior to the initiation of rescue treatment. However, if the endoscopy with biopsies cannot occur due to COVID-19 restrictions, rescue treatment should not be delayed, and these patients will be eligible for Part C. Part C treatment will be initiated per the schedule of events and only at an in-clinic visit.

Patients receiving rescue therapy may continue to receive study drug. They will remain blinded and will be asked to return to the clinic for all remaining study visits for the double-blind treatment period and the follow-up period, and participate in all assessments for these visits according to the schedule of events specified in [Table 1](#), [Table 2](#), and [Table 3](#), except for endoscopy/biopsy, as noted above. For the purpose of efficacy analyses, patients who receive rescue treatment during the study will be considered treatment failures.

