During the 24-week, placebo controlled, double-blind treatment period, clinic visits are scheduled per the schedule of events (Section 11.2). Patients and parents/caregivers will be trained on injecting study drug at the first 3 visits during the double-blind treatment period. Patients will be closely monitored at the study site at visits 3 to 6 (baseline visit, study weeks 1, 2, and 4) for a minimum of 30 minutes after the administration of study drug. During weeks when no clinic visit is scheduled, the patient or parent/caregiver will administer study drug. Doses of study drug administered at home should be administered one week after the prior dose of study drug. Study drug administration that occurs in clinic should occur per the Schedule of Events in Section 11.2. Patients and parents/caregivers who prefer to have clinic staff administer study drug may choose to have injections administered in the clinic.

The end of treatment visit for the double-blind treatment period is at week 24. The co-primary endpoints will be assessed at week 24, one week after the last dose of study drug during the double-blind treatment period.

Patients who prematurely discontinue study treatment will be encouraged to remain in the study and attend all subsequent scheduled visits.

At the end of the double-blind treatment visit (week 24), eligible patients in Part B may enter Part C, which consists of a 28-week extended active treatment period. Patients from Part B who are randomized to placebo during the double-blind treatment period will be re-randomized in a 1:1 ratio to dupilumab 300 mg QW or dupilumab 300 mg Q2W. Patients randomized to dupilumab 300 mg Q2W will also receive matching placebo alternating with dupilumab doses so the injection frequency will be identical for both groups for regimen-blinding purposes. All other patients will remain on the same dupilumab dose regimen to which they are randomized during the double-blind treatment period. Patients who do not enter Part C may enter a 12-week follow-up period.

Due to the COVID-19 pandemic, the Sponsor allows study procedures to occur outside the protocol specified timepoint and/or outside of the clinic environment and will remain in effect only for the duration of the public health emergency:

- Endoscopy with biopsies may be delayed for visit 11/week 24, visit 19/week 52, early termination, and before initiating rescue treatment

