Dilated intercellular spaces (DIS)	0	0	0
Surface epithelial alteration (SEA)	0	0	0
Dyskeratotic epithelial cells (DEC)	0	0	0
Lamina propria fibrosis (LPF)	missing	0	1
8-feature Mean Grade Score	$(3+2+2)/21=0.33$	$(3+3+2)/24=0.33$	$(3+3+3+1)/24=0.42$

Due to the anticipation that lamina propria may not be present in many biopsies, a total grade or total stage score by summing scores from the other 7 individual features will be calculated for an exploratory analysis. In the example given above, the total grade score excluding lamina propria is  $(3 + 2 + 2) + (3 + 3 + 2) + (3 + 3 + 3) = 24$ .

Esophageal biopsies will be obtained by endoscopy at the second screening visit (visit 2, day  $-21 \pm 7$ ), week 24 and week 52 (EOS) or ET visits, and immediately prior to the start of rescue medication or procedures. Patients undergoing endoscopy/biopsy prior to or due to the initiation of rescue will not undergo the scheduled endoscopy/biopsy at weeks 24 and 52.

The **other secondary** endpoints are:

- Proportion of patients achieving peak esophageal intraepithelial eosinophil count of  $<15$  eos/hpf at week 24
- Proportion of patients achieving peak esophageal intraepithelial eosinophil count of  $\leq 1$  eos/hpf at week 24

- Percent change in DSQ from baseline to week 24
- Normalized Enrichment Scores (NES) for the relative change from baseline to week 24 in the EoE diagnostic panel (EDP)
- NES of the relative change from baseline to week 24 in the type 2 inflammation signature
- Absolute change from baseline to week 24 in health-related QOL average score as measured by EoE Impact Questionnaire (EoE-IQ)
- Absolute change from baseline to week 24 in severity of EoE symptoms other than dysphagia and pain with swallowing as measured by EoE Symptom Questionnaire (EoE-SQ)
- Absolute change from baseline to week 24 in frequency of EoE symptoms other than dysphagia and pain with swallowing as measured by EoE Symptom Questionnaire (EoE-SQ)
- Proportion of patients who receive rescue medications or procedures during the 24-week placebo-controlled treatment period
- Absolute change from baseline to week 24 in esophageal distensibility plateau measured by endolumenal functional lumen imaging probe (EndoFLIP), if collected.
- All the above co-primary and secondary endpoints assessed at week 24 will be assessed at week 52 as additional secondary endpoints.

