### 5.3. Prior/Concomitant Medications/Procedures

Number and proportion of subjects taking prior/concomitant medications, prohibited medications/procedures and rescue medications/procedures will be summarized for each treatment group and study total, based on the study part specific SAFs, by ATC Level 2 and ATC Level 4, sorted by decreasing frequency of ATC Level 2 and ATC level 4 in the dupilumab treatment group.

Number and proportion of subjects taking PPIs for the treatment of EoE will be summarized by PPI therapy name.

Number and proportion of subjects undergoing prior/concomitant procedures will be summarized for each treatment group and study total, based on the study part specific SAFs, by system organ class (SOC) and preferred term (PT), and sorted by decreasing frequency of SOC and PT in the dupilumab treatment group.

In addition, the summary of prior/concomitant medications/procedures will be performed for subjects who were impacted by COVID-19 pandemic and not impacted by COVID-19 pandemic in each study period, respectively. The summary will be performed for pre-, during, and post-COVID-19 periods for subjects impacted by COVID-19, if applicable.

The detailed information of rescue medications/procedures including duration of use and incidence of use will be summarized, particularly for swallowed topical/systemic corticosteroids used to treat EoE. Kaplan Meier curves for time to first rescue use will be generated.

Separate summaries will be provided for Part B and Part C concomitant medications/procedures. For CMs/CPs taken during the follow-up period, separate summaries will be provided for patients who entered follow-up after Part C vs. patients who entered follow-up immediately after Part B. If there is a limited number of patients entering follow-up immediately after Part B, only listing will be provided.

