### 5.6.1. Analysis of Co-Primary Efficacy Variable(s)

#### Histologic response (binary endpoint)

The proportion of patients achieving a histologic response of peak esophageal intraepithelial eosinophil (eos) count (from all 3 regions) of  $\leq 6$  eos/hpf at week 24 will be analyzed using the Cochran-Mantel-Haenszel (CMH) test to assess the difference in the proportion of responders in the FAS adjusting for the randomization stratification factors (age group [ $\geq 18$  vs.  $\geq 12$  to  $< 18$  years of age] and use of PPI at randomization [yes vs. no]). Estimates of treatment difference and its 95% confidence interval will be presented.

Data may be collected after the patient discontinued treatment and will be included in the analyses.

To account for use of rescue treatment (see Section 0), patients will be considered as non-responder for all time points subsequent to the use of rescue treatment in the primary analysis.

If week 24 biopsy is performed after the date when the first dose of Part C study drug is administered, patients will be considered as non-responder in the analysis.

Due to COVID-19 restrictions, patients may postpone the week 24 visit until an in-clinic visit can be done for biopsy. Before the biopsy procedure could be performed, study drug would be shipped to patients directly to enable them to extend their current assigned dose regimen of study drug. The data from those delayed week 24 visits will be used in the primary analysis as long as the patients keep the extended dosing before biopsy. However, for patients in whom extended dosing due to COVID-19 is interrupted (i.e. 2 or more consecutive doses or 5 or more doses in total missing during extended dosing period), their week 24 biopsy data will be set to missing and then imputed using MI.

Missing data at week 24 will be handled according to the reason for missingness as follows:

- If the peak esophageal intraepithelial eosinophil count at week 24 is missing due to COVID-19 pandemic, the data will be imputed by multiple imputation (MI) using a random seed number of 6681774 for 10 times based on patients who have non-missing eosinophil counts at week 24. The MI will utilize the regression method with treatment group, randomization stratification, baseline eosinophil count, and week 24 eosinophil count included in the regression model. The imputed week 24 eosinophil counts will

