determine whether that patient will be classified as a responder or non-responder. The results from each imputed dataset will be combined according to Rubin's formula (Rubin, 1987).

- If a patient has missing value for the histological response (peak esophageal intraepithelial eosinophil count) at week 24 due to reasons not related to the COVID-19 pandemic, the patient will be classified as a non-responder at week 24.

The complete dataset after the above steps will be analyzed by the CMH test.

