**11.1.2. Summary of Efficacy Analyses**

Endpoint	Analysis Populations	Primary Statistical Method	Supportive/Sensitive Statistical Method	Subgroup Analysis	Other Analyses
Primary Endpoints					
Proportion of patients achieving a histologic response of esophageal intraepithelial eosinophil count of $\leq 6$ eos/hpf at week 24	FAS	Cochran-Mantel-Haenszel test / MI for missing due to the COVID-19 pandemic, otherwise define missing as non-responder	Cochran-Mantel-Haenszel test on LOCF-MI, valid week 24, week 24 regardless of any delay	Yes	Histogram
Absolute change from baseline in the DSQ total score at week 24	FAS	MI+ANCOVA	ANCOVA with LOCF, WOCF, requiring 4/7 diary entries per week	Yes	Line plot
Secondary Endpoints					
Secondary continuous variables	FAS	MI+ANCOVA for endpoints measured repeatedly (eg, DSQ); ANCOVA with WOCF-MI for endpoints measured only once post-baseline in Part B (eg, peak eos count)	ANCOVA with LOCF, LOCF-MI	Yes for key secondary efficacy	Line plot
Secondary binary variables	FAS	Cochran-Mantel-Haenszel test / MI for missing due to the COVID-19 pandemic, otherwise define missing as non-responder	Cochran-Mantel-Haenszel test on LOCF-MI	No	Histogram

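### The rescue-use secondary endpoint inherits a missing-data rule written for histologic response; the rule does not fit it and leaves the coding of patients who withdraw undefined

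*SAP*

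**What the plan says.** SAP section 4.4.2 lists among the other secondary endpoints: "Proportion of patients who receive rescue medications or procedures during the 24-week placebo-controlled treatment period". The event is unfavourable and is counted over a period, not read at one visit.

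Three places set the analysis of binary secondary endpoints:

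- SAP section 5.6.2: "Secondary efficacy endpoints that measure binary responses at week 24 will be analyzed in the same fashion as the co-primary endpoint of histologic response", with the missing-data method included.
- Appendix 11.1.1: a row for binary endpoints that points to the same histologic-response analysis.
- Appendix 11.1.2: a row for secondary binary variables in the FAS, using a Cochran-Mantel-Haenszel (CMH) test and "MI for missing due to the COVID-19 pandemic, otherwise define missing as non-responder". It has no time limit and no exception.

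The parent method is in SAP section 5.6.1. After rescue, "patients will be considered as non-responder for all time points subsequent to the use of rescue treatment in the primary analysis". If the count is missing for reasons unrelated to COVID-19, "the patient will be classified as a non-responder at week 24". If it is missing because of COVID-19, the week-24 eosinophil count is imputed by regression and then classified.

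Section 5.6.2 does make exceptions for other secondary endpoints: a Wilcoxon test for the transcriptome scores and descriptive statistics for EndoFLIP. It makes none for rescue use. The only other rescue analyses are the medication and procedure summaries in SAP section 5.3, based on the SAF, where "Kaplan Meier curves for time to first rescue use will be generated".

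**The concern.** Treating missing as non-response is a cautious convention when the event is good. Here the event is rescue, and each inherited element fails:

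- **Rescue as non-response.** For this endpoint, that is the outcome itself, so the intercurrent-event rule is circular.
- **COVID-19 imputation.** The model returns an eosinophil count, from which no rescue status can be derived.
- **Other missing data as non-response.** The SAP does not say whether the non-responder is the rescued or the unrescued patient.

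Two programmers could follow the SAP and code the same early leaver in opposite ways. Either coding makes the between-arm comparison depend on who leaves. Patients who leave because of poor control may also be those most likely to have needed rescue.

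**Working it through.** The documents state no rescue rate, power or other figure for this endpoint, so there is nothing of the plan's own to reproduce.

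**Inputs from the documents:** 70 patients per arm and 15% dropout overall (SAP section 2.3). **Assumed inputs:** the true rescue risk p and the dropout in each arm, d_A (active) and d_P (placebo).

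**Between-arm effect.** Let p be the same in both arms. Suppose no leaver's rescue status is observed (an upper bound on what is lost) and leavers have the same risk as stayers.

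- Missing coded as not rescued: apparent rate p(1 - d), so the spurious active-minus-placebo difference is p(d_P - d_A).
- Missing coded as rescued: apparent rate d + p(1 - d), so the spurious difference is (1 - p)(d_A - d_P).

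With d_A = 20% and d_P = 10%, for example at p = 10%: 0.10 × (0.10 - 0.20) = -1.0 point, and 0.90 × (0.20 - 0.10) = +9.0 points.

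| p | Not rescued: difference | False nominal win for active | Rescued: difference | False nominal loss for active |
|---|---|---|---|---|
| 5% | -0.5 | 3.2% | +9.5 | 29.9% |
| 10% | -1.0 | 4.1% | +9.0 | 24.4% |
| 20% | -2.0 | 5.0% | +8.0 | 17.5% |
| 40% | -4.0 | 7.2% | +6.0 | 10.8% |

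Differences are in percentage points. The probabilities come from exact binomial enumeration of an unstratified chi-square test at 70 per arm, standing in for CMH. The nominal value in each direction is 2.5%. With 15% dropout in both arms, the difference is 0 under either coding.

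**One-arm understatement if missing means not rescued.** Take d = 0.15, dropout uniform over 24 weeks, constant rescue hazard λ = -ln(1 - p)/24 and S(t) = exp(-λt). The share of events lost is d × mean[S(t)(1 - exp(-kλ(24 - t)))], where k multiplies the hazard after dropout. Writing L = -ln(1 - p):

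- k = 1: d[p/L - (1 - p)]. At p = 10%, 0.15 × (0.9491 - 0.9000) = 0.0074.
- k = 5: d[p/L - ((1 - p) - (1 - p)^5)/(4L)]. At p = 10%, 0.15 × (0.9491 - 0.7344) = 0.0322.

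| p | k = 1 | k = 5 |
|---|---|---|
| 5% | 0.4 points | 1.7 points |
| 10% | 0.7 points | 3.2 points |
| 20% | 1.4 points | 5.5 points |

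If the hazard is five times higher throughout, before dropout as well, the losses are 1.6, 2.8 and 4.1 points.

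**The case against.** **The main text may not reach this endpoint.** Section 5.6.2 speaks of responses at week 24, whereas rescue is an event over a period, taken from medication and procedure records. That is a fair reading of the sentence. It does not apply to the Appendix 11.1.2 row, which has no such limit. If the binary rule is taken not to apply, the endpoint has no specified efficacy analysis, so the SAP needs a sentence either way.

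**The direction of bias is not stated.** A reader might infer that dropouts count as not needing rescue, so that the plan rewards the arm with more dropout. The documents do not support this. Nowhere is a missing patient coded as not rescued. Where the terms are linked, they point the other way: SAP section 5.6.1 makes the rescued patient a non-responder, and Protocol section 7.3 says "patients who receive rescue treatment during the study will be considered treatment failures". On that usage, leavers would be grouped with rescued patients. This objection stands in full, and the defect is therefore an undefined code.

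**Exposure is limited.** "Patients who prematurely discontinue study treatment will be encouraged to remain in the study and attend all subsequent scheduled visits" (SAP section 2.4). Concomitant medications and procedures are recorded until the end-of-study visit (SAP section 4.3) and at the early termination visit (SAP Table 8). Rescue is therefore unobserved mainly after study withdrawal, and 15% is a planning assumption. This also stands.

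**A censored analysis has its own weakness.** Kaplan-Meier and log-rank methods assume that censoring is unrelated to rescue risk, and patients leaving for poor control would break that assumption. The planned curves do not settle the matter: section 5.3 gives no censoring rule, no between-arm estimate and no confidence interval. Sensitivity analyses are needed with any choice.

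**Conclusion.** The inherited rule is unsuitable for rescue use, and the coding of withdrawals is undefined. That follows from the text alone. The size of the effect rests on assumed rescue and dropout rates. At 20% against 10% dropout, the spurious difference is at most 4 points in favour of the arm with more dropout under one coding, and 6 to 9.5 points against it under the other. It is zero if dropout and true rescue risk are equal across arms. The documents do not establish which arm would benefit.

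The priority is minor. Rescue use is not a key secondary endpoint and is not among the 18 steps in SAP section 5.6.3, so no alpha-controlled conclusion depends on it.

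**What to change.** Exempt rescue use from the binary rule in SAP section 5.6.2 and in both appendix tables, and specify:

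1. **Event:** first adjudicated rescue medication or procedure in Part B, using the blinded adjudication already planned in SAP section 4.3.
2. **Estimate:** Kaplan-Meier proportion with rescue by week 24 in the FAS, censored at last Part B contact, with the difference of each dupilumab arm from placebo and its 95% CI.
3. **Test:** log-rank stratified by age group and PPI use at randomization, with a nominal p-value.
4. **Sensitivity analyses, because censoring may be informative:** study withdrawals before week 24 without rescue coded as all rescued, then as none rescued; and withdrawal for lack of efficacy counted as an event.

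The cost is SAP wording and limited programming, since time-to-first-rescue curves are already planned. No new data are needed and the testing hierarchy is unchanged.

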For transcriptome endpoints, the Wilcoxon rank-sum test will be used for patients with NES data collected to test if the difference in median NES of the relative change from baseline to week 24 between the dupilumab and placebo groups is statistically significant. Missing NES data will be imputed by LOCF. P-values will be reported.

The endpoints from EndoFLIP will be summarized with descriptive statistics using all observed data.

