If a patient has missing value for the histological response (peak esophageal intraepithelial eosinophil count ≤6 eos/hpf) at week 24, the patient will be classified as a non-responder at week 24.

If a patient has missing value for the DSQ total score at week 24, the missing data will be imputed by MI based on similar patients who remained in the trial with observed values relevant to analysis. Similarity is based on randomized

treatment group, baseline value, stratification factors, and available post-baseline values.

Sensitivity analyses will assess alternative methods to impute missing data. For the eosinophil responder analysis, sensitivity methods may include utilizing peak eosinophil values from imputations to determine responder status. Sensitivity analyses will also include an analysis without setting data post-rescue to missing.

Secondary Efficacy Analysis (Part A and Part B):

Secondary efficacy endpoints will be analyzed in the same fashion as the co-primary endpoints depending on the type of data, unless otherwise specified.

For continuous efficacy data that are scheduled to be measured only once post-baseline at week 24, missing values at week 24 will be imputed with patient's baseline value or the available post-baseline value, whichever is worse, ie, a worst observation carried forward (WOCF) approach.

Subgroup analysis (eg, by age group) will also be performed.

Secondary Efficacy Analysis (Part C):

Efficacy endpoints in Part C will be summarized with descriptive statistics by treatment received in Part C. Inferential statistics will only be provided as needed.

Multiplicity Considerations:

Part A and Part B will have separate and independent 2-sided alpha level of 0.05.

Part A: Statistical significance of the co-primary endpoints at the 2-sided Type I error rate of 5% will be required before drawing inferential conclusions about any secondary efficacy endpoints.

Part B: The co-primary endpoints will be tested for the comparison of dupilumab QW dose regimen to placebo first and if both endpoints are statistically significant, the testing will proceed to the co-primary endpoints of dupilumab Q2W, or the secondary endpoints of dupilumab QW, with the exact order to be specified in Part B statistical analysis plan (SAP).

Safety Analysis:

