4.2.2. Secondary Endpoints

The key secondary endpoints for both Parts A and B of the study are:

- Absolute change in EoE-EREFS from baseline to week 24
- Percent change in peak esophageal intraepithelial eosinophil count (eos/hpf) from baseline to week 24
- Absolute change in EoE Grade Score from the EoE Histology Scoring System (EoEHSS) from baseline to week 24
- Absolute change in EoE Stage Score from the EoEHSS from baseline to week 24

The other secondary endpoints are:

- Proportion of patients achieving peak esophageal intraepithelial eosinophil count of < 15 eos/hpf at week 24
- Proportion of patients achieving peak esophageal intraepithelial eosinophil count of ≤ 1 eos/hpf at week 24
- Percent change in DSQ from baseline to week 24
- Normalized Enrichment Scores (NES) for the relative change from baseline to week 24 in the EoE diagnostic panel (EDP) transcriptome signature
- NES for the relative change from baseline to week 24 in the type 2 inflammation transcriptome signature
- Absolute change from baseline to week 24 in health-related QOL as measured by EoE Impact Questionnaire (EoE-IQ)
- Absolute change from baseline to week 24 in severity and/or frequency of EoE symptoms other than dysphagia
- Proportion of patients who receive rescue medications or procedures during the 24-week placebo-controlled treatment period
- Absolute change from baseline in esophageal distensibility plateau measured by functional lumen imaging, if collected, at week 24.

Note: All the above co-primary and secondary endpoints assessed at week 24 will be assessed at week 52 as secondary endpoints and summarized with descriptive statistics

based on the treatment assignment in the double-blind treatment period as well as the extended active treatment assignment for patients previously in the placebo group.

Both co-primary and all secondary endpoints will be assessed at week 24 and week 52 in adult and adolescent patients with EoE who have previously received swallowed topical corticosteroids.

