10.4.3.2. Secondary Efficacy Analysis

10.4.3.2.1. Analysis of Secondary Efficacy Endpoints in Part A and Part B

Binary endpoints:

Secondary efficacy endpoints that measure binary responses at week 24 will be analyzed in the same fashion as the co-primary endpoint of histologic response of peak esophageal intraepithelial

eosinophil count of ≤ 6 eos/hpf, including the method to handle missing data and planned sensitivity analyses.

Continuous endpoints:

For Part A enrolled patients, EoE-EREFS assessed by investigators will be used in the analysis (no centralized readings available). For Part B enrolled patients, the primary analysis of EoE-EREFS will be based on centralized readings, if available. If the centralized reading is not available, the EoE-EREFS performed by the investigator will be used for analysis.

Continuous secondary efficacy endpoints at week 24 will be analyzed using ANCOVA in a similar fashion to the co-primary endpoint of change from baseline in the DSQ total score.

For continuous efficacy data that are scheduled to be measured repeatedly post-baseline up to week 24 (eg, percent change in DSQ score from baseline to week 24), missing data will be imputed by MI as described in the primary efficacy analysis of the DSQ co-primary endpoint. Sensitivity analyses similar to those specified for the DSQ co-primary endpoint will be conducted.

For continuous efficacy data that are to be measured only once post-baseline up to week 24 (eg, percent change in peak eos/hpf from baseline to week 24), missing values at week 24 will be imputed with patient's baseline value or the available post-baseline value, whichever is worse, ie, a worst observation carried forward (WOCF) approach. MI approach is not suitable for handling missing data in this case due to the fact that the complete case patients will not have measurements available at the time points when measurements are obtained for ET patients (designed to be at their ET visits) to enable the imputation of week 24 missing values for early terminated patients. A sensitivity analysis, using the LOCF approach to impute missing values at week 24, will be performed.

To account for use of rescue treatment, data will be imputed by MI for continuous endpoints repeatedly measured or by WOCF for continuous endpoints measured only once up to week 24 visit after the use of rescue treatment.

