### 1.2.3. Modifications from the Statistical Section in the Final Protocol

The Part B per protocol analysis set (PPS) is removed since estimands are constructed, with aligned method of analysis, that better address the objective and analysis of PPS might not add additional insights.

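### SAP 5.6.2 summarizes the week 24 distensibility plateau, a listed secondary endpoint, by arm only; it plans no difference from placebo and does not declare the departure from the protocol's ANCOVA rule

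*SAP*

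**What the plan says.** **Endpoint.** Protocol 4.2.2 lists, among the other secondary endpoints, "Absolute change from baseline in esophageal distensibility plateau measured by functional lumen imaging, if collected, at week 24". SAP 4.4.2 keeps it for Part B: "Absolute change from baseline to week 24 in esophageal distensibility plateau measured by endolumenal functional lumen imaging probe (EndoFLIP), if collected".

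**Protocol method.** Section 10.4.3.2.1 states: "Continuous secondary efficacy endpoints at week 24 will be analyzed using ANCOVA in a similar fashion to the co-primary endpoint". For endpoints measured once after baseline, a missing week 24 value is replaced by the baseline or available post-baseline value, "whichever is worse, ie, a worst observation carried forward (WOCF) approach". The same replacement applies after rescue. The only endpoints that section gives a different test are the transcriptome scores (Wilcoxon rank-sum).

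**SAP method.** SAP 5.6.2 repeats the ANCOVA rule. For endpoints measured once, it imputes COVID-related missing values by MI and other missing values by WOCF. The table in SAP 11.1.2 applies this to secondary continuous variables without excepting EndoFLIP. Later in SAP 5.6.2 comes: "The endpoints from EndoFLIP will be summarized with descriptive statistics using all observed data".

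**Declared changes.** SAP 1.2.3 lists one modification from the protocol: "The Part B per protocol analysis set (PPS) is removed since estimands are constructed".

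**Data source.** Protocol 8.2.2.1 describes an optional substudy in about 150 adults at selected North American sites, with readings at screening, week 24 and week 52.

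**The concern.** This endpoint comes from a randomized comparison and has a pre-treatment reading, and the protocol gives a method for its class. The SAP replaces that method with a summary by arm and gives no reason.

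The protocol treats distensibility as clinically informative. Section 3.2.3.1 cites improved distensibility in the phase 2 dupilumab study, and 8.2.2.1 cites its association with food impaction and need for dilation. Readers will therefore compare the arm means whether or not a contrast is planned. They would do so without adjustment for chance baseline imbalance, which can be appreciable in a small subset.

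Using observed data only also has a cost. Under protocol 7.3, a patient who has an endoscopy before rescue does not have the scheduled week 24 endoscopy. Missing week 24 readings are then related to poor outcome, and a summary of observed values leaves those patients out.

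**Working it through.** The plan states no sample size, SD, effect size or power for EndoFLIP, so there is no figure to reproduce. The main check is textual.

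| Item | Protocol 10.4.3.2.1 | SAP 5.6.2 general rule and 11.1.2 | SAP 5.6.2 EndoFLIP sentence |
|---|---|---|---|
| Method at week 24 | ANCOVA | ANCOVA | Descriptive |
| Covariates | Strata and baseline, as for the DSQ co-primary | Same | None |
| Missing week 24 value | WOCF | MI if COVID-related, otherwise WOCF | None; observed data only |
| After rescue | WOCF | Set to missing, then as above | Observed values kept |
| Difference from placebo | Yes | Yes | Not planned |
| Listed in SAP 1.2.3 | n/a | n/a | No |

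The EndoFLIP sentence thus departs from the protocol body and from the SAP's own general rule and summary table.

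**What the summaries still give.** SAP section 5 requires results by treatment group, placebo included, with n, mean and SD. A reader can therefore form m1 − m2 with standard error √(s1²/n1 + s2²/n2). What is missing is a planned contrast that adjusts for baseline and has a stated rule for rescue and missing values.

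**Would a contrast be informative?** The documents do not split the 150 adults between Parts A and B, so the numbers per Part B arm below are assumptions.

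- All 150 in Part B, allocated 1:1:1: 150/3 = 50 per arm. With the 15% dropout of SAP 2.3: 50 × 0.85 = 42.5, taken as 42.
- Spread in proportion to planned enrolment of 80 and 210: 150 × 210/290 = 108.6, and 108.6/3 = 36 per arm. With 15% loss: 36.2 × 0.85 = 30.8, taken as 30.
- Low case: 20 per arm, the size SAP 3.5 gives as an example of a subgroup too small to analyse.

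Half-width of the unadjusted 95% interval, in SD units: t(0.975, 2n − 2) × √(2/n). Difference detectable with 80% power, two-sided 5%: (1.96 + 0.84) × √(2/n). Adjustment for a baseline with correlation r to the week 24 value multiplies the detectable difference by √(1 − r²). The SD is that of the week 24 value.

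| n per arm | 95% half-width, unadjusted (SD) | Detectable, unadjusted (SD) | r = 0.3 | r = 0.5 | r = 0.7 |
|---|---|---|---|---|---|
| 50 | 0.40 | 0.56 | 0.53 | 0.49 | 0.40 |
| 42 | 0.43 | 0.61 | 0.58 | 0.53 | 0.44 |
| 36 | 0.47 | 0.66 | 0.63 | 0.57 | 0.47 |
| 30 | 0.52 | 0.72 | 0.69 | 0.63 | 0.52 |
| 20 | 0.64 | 0.89 | 0.85 | 0.77 | 0.63 |

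**Illustration of baseline adjustment.** With equal variances at baseline and week 24, a change score has variance proportional to 2(1 − r) and ANCOVA to 1 − r². Their ratio is (1 + r)/2, or 0.65, 0.75 and 0.85 at assumed r = 0.3, 0.5 and 0.7.

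**The case against.** The strongest defence is that the SAP was free to do this. The protocol synopsis says: "Secondary efficacy endpoints will be analyzed in the same fashion as the co-primary endpoints depending on the type of data, unless otherwise specified". Protocol section 10 allows the part-specific SAP to change for unexpected issues in execution and data. The endpoint is conditional on collection, and the readings come from an optional, adults-only subset at selected sites. The protocol's ANCOVA is written for all randomized patients and cannot be carried over unchanged to that subset. A descriptive summary is a defensible choice for such data.

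Much of this stands: the choice is permissible. It does not explain why the choice is undeclared. The body of the protocol has no EndoFLIP exception, the SAP gives no reason, and SAP 1.2.3 is where the change belongs. Nor does subset status settle the method. SAP 5.6.5 applies the co-primary and secondary methods to exploratory scores such as TNSS, POEM and ACQ-5, which are collected only in patients with the relevant comorbidity.

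Three stronger readings are tempting, and the documents do not support them:

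- *That there is no comparison with placebo at all.* Arm summaries including placebo are produced, and an unadjusted difference can be derived from them.
- *That the baseline reading is wasted.* The endpoint is a change score, so each patient's baseline enters the outcome. Only covariate and stratum adjustment is absent.
- *That 15% to 35% of the variance is needlessly given up.* That range compares ANCOVA with a change-score contrast that the SAP does not plan, and it rests on assumed correlations and equal variances. It is illustrative only.

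**Conclusion.** The point holds as an undeclared departure and a missed planned contrast. For week 24 change in distensibility plateau in Part B, the SAP produces no planned dupilumab-placebo difference, confidence interval or baseline adjustment. This differs from protocol 10.4.3.2.1 and from the SAP's own rule in 5.6.2 and 11.1.2, and SAP 1.2.3 does not say so.

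The consequence is limited. The endpoint is neither a key secondary endpoint nor one of the 18 steps in SAP 5.6.3, so a reader should not infer any effect on the co-primary conclusions or on type I error control.

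Whether a contrast would be precise cannot be settled from the documents. At 30 to 50 patients per arm the unadjusted interval would have a half-width of 0.40 to 0.52 SD; at 20 per arm it would be 0.64 SD. These figures rest on the assumed split of about 150 adults, and no SD in clinical units is given. The conclusion covers Part B only, since the Part A SAP is not among the documents. It is an improvement worth considering.

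**What to change.** Replace the EndoFLIP sentence in SAP 5.6.2 with a specification along these lines:

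- **Population:** randomized Part B patients with a baseline EndoFLIP reading.
- **Model:** ANCOVA of week 24 change in distensibility plateau on treatment group, baseline value and PPI use at randomization. The age stratum is omitted because the substudy is in adults and it would be constant.
- **Rescue and missing values:** the SAP 5.6.2 rule for endpoints measured once (data after rescue set to missing; MI for COVID-related missing values, WOCF otherwise). State that a lower plateau is the worse value, in line with protocol 8.2.2.1, which reports reduced plateaus in EoE. Give an observed-case analysis as supportive.
- **Reporting:** each dupilumab-placebo difference with its 95% CI and a nominal p-value, outside the hierarchy.
- **Unchanged:** RD40, RD30 and week 52 stay descriptive. RD40 and RD30 are not listed secondary endpoints.

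List any remaining departure from the protocol in SAP 1.2.3, with its reason. If the sponsor prefers to keep the descriptive summary, the minimum is to declare and justify it there and to add the exception to the SAP 5.6.2 general rule and the 11.1.2 table.

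The cost is a short SAP paragraph and one table, with no new data collection. The drawback is that the interval may be wide if few Part B patients have readings; showing the interval makes that uncertainty explicit.
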